1 SOURCE DOCUMENTS

The Statistical Analysis Plan (SAP) was written based on the following documentation:

| Document | Date | Version |
|------------------------------------|-------------------|-------------|
| Protocol | 16 October 2015 | Amendment 1 |
| Electronic Case Report Form (eCRF) | 18 September 2015 | Version 1.0 |

2 PROTOCOL DETAILS

2.1 Study Objectives

2.1.1 Study Objectives

2.1.1.1 Primary Objective

The primary objective of this study is to demonstrate the superiority of sotagliflozin 400 mg versus placebo in the proportion of patients with glycosylated hemoglobin A1C (A1C) <7.0% at Week 24 and no episode of severe hypoglycemia (SH) and no episode of diabetic ketoacidosis (DKA) after randomization.

2.1.1.2 Secondary Objectives

Secondary objectives of this study are to evaluate the change from Baseline of sotagliflozin versus placebo in a hierarchical order on the following:

- A1C
- Body weight
- Systolic blood pressure (SBP)
- Bolus insulin dose

2.1.1.3 Other Objectives

Other objectives of this study are:

To compare changes in several parameters in response to sotagliflozin versus placebo, as assessed by evaluations with specified cut points, and at specified time intervals during the 24-week Double-blind Treatment Period including:

- Parameters assessed as secondary objectives (A1C, body weight, SBP, bolus insulin dose)
- Proportion of patients with A1C reduction $\geq 0.4\%$ and no increase in body weight
- Proportion of patients with A1C reduction $\geq 0.5\%$ and no episode of SH
- Proportion of patients meeting success criteria for A1C and insulin
- Fasting plasma glucose (FPG)
- Total and basal (or non-bolus) insulin dose
- Diastolic blood pressure (DBP)
- Hypoglycemic events
- Measures of kidney function
- Patient-reported satiety (substudy)
- Safety of sotagliflozin 400 mg versus placebo

Statistical Analysis Plan

Version: Final 1.0

Lexicon Pharmaceuticals Protocol No. LX 4211.1-312-T1DM

Date of Issue: 29 MAR 2017

Covance Study ID: 000000145143

2.2 Overall Study Design

This study is a Phase 3, multicenter, randomized, double-blind, placebo-controlled, parallel-group study.

Adult patients with type 1 diabetes mellitus (T1D) and body mass index (BMI) ≥ 18.5 kg/m² with inadequate glycemic control with insulin therapy (administered by subcutaneous injections or continuous subcutaneous insulin infusion [CSII]) are eligible for enrollment in this study if they meet all inclusion and no exclusion criteria.

A total of 1400 patients will be randomly assigned 1:1 between the following 2 treatment groups, stratified by BMI at Screening (<25 kg/m², ≥ 25 kg/m²), Week -2 A1C ($\leq 9\%$, $>9\%$) and use of CSII at Screening (Yes, No):

- Sotagliflozin 400 mg as two (2) 200-mg tablets, once daily, before the first meal of the day
- Placebo as two (2) placebo tablets (identical to sotagliflozin in appearance), once daily, before the first meal of the day

Patients will continue treatment with insulin(s) or insulin analog(s) during the study.

During the study, self-monitored blood glucose (SMBG) values will be reviewed by the Investigator and insulin doses will be adjusted if the SMBG trends do not meet standard of care T1D target goals.

Suggested insulin titration algorithms are provided in the Site File Notebook. These algorithms may be modified based on the Investigator's clinical assessment.

Patients will participate in the study for approximately 32 weeks. The study includes a Screening Period of up to 2 weeks, followed by a 2-week single-blind placebo Run-in Period, a 24-week Double-blind Treatment Period, and a 30-day Follow-up Period.

Efficacy and safety assessments will be performed according to the study schedule.

This study will also include a substudy designed to evaluate satiety (appetite) in a subset of enrolled patients. Up to 280 patients (140 per treatment group) will be recruited for this substudy.

The study design is summarized in [Figure 2.2-1](#).

[figure not shown]

Figure 2.2-1 Study Schema

COVANCE INC. CONFIDENTIAL

Statistical Analysis Plan

Version: Final 1.0

Lexicon Pharmaceuticals Protocol No. LX 4211.1-312-T1DM

Date of Issue: 29 MAR 2017

Covance Study ID: 000000145143

Adjudication of all deaths, event(s) of special interest (EOSIs), including major adverse cardiovascular events (MACE)/selected cardiovascular (CV) events, clinical or laboratory findings associated with drug-induced liver injury (DILI), DKA (including metabolic acidosis), and SH episodes (as well as hypoglycemia reported as a serious adverse event [SAE]) will be performed in a blinded manner by independent Clinical Endpoint Committee(s) (CEC[s]) composed of the appropriate experts. Details will be provided in the CEC(s) Charter(s).

An independent Data Monitoring Committee (DMC) will meet on a regular basis to review accumulating clinical safety data. Details will be provided in the DMC Charter.

2.3 Sample Size and Power

The sample size will be based on satisfying design assumptions made for the primary efficacy endpoint. The primary efficacy endpoint is a binomial proportion, a composite measure of glycemic control and safety. We have assumed that the majority of treatment effect will be observed in the glycemic control portion of the endpoint and for planning purposes, the rates of SH and DKA will be equal in both treatment groups. Little data are available to estimate the <7% A1C component of the endpoint in this patient population. Data reviewed from the LX4211.1-202 Phase 2 trial in type 2 diabetes mellitus (T2DM) and from other pertinent literature sources suggests that a difference between treatment groups of at least 0.15 may be expected for this variable. We will assume this effect size for the primary endpoint, but will perform an adjustment for the expected proportion of patients not having a DKA or SH event. A conservative assumption is made that the rates of DKA and SH are independent and their union is estimated to be ≤ 0.15 . It is expected that 0.85 of the patients will not have a DKA or a severe hypoglycemic event over the course of the study. Adjusting the 0.15 effect size estimate by this value yields a target effect size for the primary endpoint ≈ 0.12 . Since the underlying placebo rate is unknown for the composite outcome, we will assume a maximum variance construct under the alternative hypothesis for binomial proportions to estimate the sample size (ie, the mean of the pooled responses rates is 0.50). Assuming a 2-sided test with $\alpha = 0.05$ and 90% power, 380 patients are needed per treatment group to detect a difference in binomial proportions of at least 0.12 for the primary endpoint. The sample size estimate will be adjusted for dropouts in a manner to reflect that the primary analysis will be conducted in the modified Intent-to-Treat (mITT) patients. Dropouts are expected to be primarily a function of noncompliance: patients stopping early their randomized treatment, but followed to the 24-week visit. It is further assumed that the dropped (noncompliant) sotagliflozin patients will respond as the placebo patients and that there will be no drop-in patients in the placebo group. These assumptions net an adjusted effect size for detection of $0.12 \times (1-0.20) \approx 0.10$, where the dropout rate over 24 weeks is assumed to be 20%. Based on this adjusted effect size, 544 patients are required per treatment group, for a total of 1088 patients across the 2 treatment groups.

The occurrence of SH is an important safety component of the primary endpoint. It is desirable that the study sample includes enough patients so that a reliable estimate of a treatment difference can be obtained for this outcome. Based on a literature review, it seems reasonable to assume that the rate of SH, defined as the number of patients experiencing at least 1 such episode divided by the number of mITT patients (ie, a binomial proportion), is ≤ 0.10 over a 24-week period. We will assume this rate is the same in both treatment groups, yielding an expected difference of 0.0. A 2-sided, 95% confidence interval (CI) based on normal approximation methods and corrected for continuity is associated with a distance value (ω) of 0.033 for a sample size of 700 patients per group; ω is the extended distance from the observed difference in one or both directions. The upper bound of this CI will exclude values greater than 0.05; ie, a 50% increase in the expected placebo rate.

Statistical Analysis Plan

Version: Final 1.0

Lexicon Pharmaceuticals Protocol No. LX 4211.1-312-T1DM

Date of Issue: 29 MAR 2017

Covance Study ID: 000000145143

Based on the considerations mentioned above, a sample size of 700 patients per treatment group (1400 total patients) seems to be an appropriate target for the study.

For the satiety substudy, assuming a dropout rate of 20% over the course of the study, a sample size of approximately 224 patients (112 per treatment group) demonstrating a change greater than 30% would be necessary to obtain statistical power at the recommended 80% level ($\alpha = 0.05$). To achieve this number of patients for evaluation, 280 patients will be recruited to participate in the substudy.

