10.4.3 Safety Analyses

Safety analysis will primarily involve examination of descriptive statistics and individual patient listings for any effects of study treatment on clinical tolerability and safety. Summaries will be prepared by treatment group and, as needed, by clinic visit. These

summaries will be based on the Safety population and other subpopulations as needed. All safety data (AEs, EOSI, laboratory test results, vital signs, ECG results, and physical examinations) will be provided in listings.

The evaluation of AEs is described in [Section 10.4.3.1](#).

Vital signs, physical examination findings, laboratory results, and ECGs will be summarized descriptively at each time point. Actual and change from Baseline data will be calculated and summarized. In addition, shift table analyses will be presented for the laboratory data.

The analysis of hypoglycemic events will be conducted per the definitions provided in [Section 9.5.1](#) and methods described for binary, continuous, and other variables in [Section 10.4.1](#). Since these data also serve as a measure of safety, additional analyses will be conducted. The first analysis will be performed using CMH tests stratified by the randomization factors at each clinic visit. These tests will provide inferential and descriptive summaries of the relative risk estimate for each of the 2 hypoglycemic event definitions: ≤ 70 mg/dL and ≤ 55 mg/dL by SMBG. The patient incidence of these hypoglycemic events will be counted over the week prior to the scheduled clinic visit used in the analysis. The second analysis of these data will examine the relative risk for each of the hypoglycemic event definitions over the entire Treatment Period by use of a generalized linear model (GLM). The GLM will include fixed, categorical effects of treatment; BMI at Screening (< 25 kg/m², ≥ 25 kg/m²), Week -2 A1C ($\leq 9\%$, $> 9\%$), use of CSII at Screening (Yes, No), and an offset term for study duration. The events will be modeled as a negative binomial process.

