6.8 Efficacy

For binary efficacy endpoints estimated as binomial proportions, the frequency and percentage of patients achieving the outcome will be presented by treatment group at each assessed study week. The primary analysis of these endpoints will use a Cochran-Mantel-Haenszel (CMH) test stratified by the different levels of the randomization stratification factors of BMI at Screening (<25 kg/m², ≥25 kg/m²), Week -2 A1C (≤9%, >9%), and use of CSII at Screening (Yes, No). The treatment group comparisons will be performed at Week 24 only. At other assessed study weeks, only descriptive statistics will be used to summarize the data. Point estimates of treatment effect and 2-sided 95% confidence limits (CLs) of the treatment effect (ie, LX4211 minus placebo) will be calculated at Week 24. The 95% CLs will be based on normal approximation methods using a continuity correction factor. Missing observations at Week 24 will be imputed as non-responders (ie, NRI); only the observed data will be summarized at the earlier study weeks. Endpoints comprised of multiple outcomes will use descriptive methods to summarize each component by treatment group at each study week.

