6.8.1 Primary Efficacy Analysis

The primary efficacy endpoint is the proportion of patients with A1C $< 7.0\%$ at Week 24 and no episode of SH and no episode of DKA from randomization to Week 24. The analysis of this endpoint will be based upon the mITT population. The frequency and percentage of patients with A1C $< 7.0\%$ at Week 24 and no episode of SH or episode of DKA from randomization to Week 24 will be presented by treatment group. For this endpoint, only positively adjudicated SH and DKA events will be assessed over the cumulative randomized 24-week Double-blind Treatment Period. The cut-off dates for the inclusion of SH and DKA events, along with other EOSIs, are described in detail in [Section 6.9.2](#). In brief, the cut-off date is the date of the last dose of double-blind study drug for SH events and 30 days after the date of the last dose of study drug for DKA.

Analysis of the primary efficacy endpoint at Week 24 will be performed using the CMH test and 95% CLs based on normal approximation methods with a continuity correction factor, as described in [Section 6.8](#) for binary efficacy endpoints. The individual components of the endpoint will be summarized separately using descriptive methods. Each of these components will be expressed as a binomial proportion: proportion of patients with A1C $< 7.0\%$ at Week 24, proportion of patients with no episodes of DKA from randomization to Week 24, and proportion of patients with no episodes of SH from randomization to Week 24.

Bar charts displaying proportions of patients with A1C $< 7.0\%$ at Week 24 and no episode of SH or episode of DKA will be presented from randomization to Week 24 by treatment groups.

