Hypoglycemia will be summarized as the incidence of patients (%) with at least 1 hypoglycemic event, number of hypoglycemic events per patient per year of exposure, and the number of hypoglycemic events per patient per day, by treatment group, separately for the Baseline Period (ie., 2-week placebo Run-in Period), Double-blind Treatment Period (including only those events that occur between date and time of first dose and date of last dose of double-blind study drug) and Follow-up Period (including only those events that occur after the date of last dose of double-blind study drug and on or before the 30-Day Follow-up). The incidence rate of nocturnal hypoglycemic events by time, nocturnal hypoglycemic events by sleep status, and diurnal hypoglycemic events will be presented. Similarly, total documented hypoglycemia (symptomatic and asymptomatic), documented symptomatic hypoglycemia, documented asymptomatic hypoglycemia, total hypoglycemic events (ie, SH or documented hypoglycemia), SH events, and positively adjudicated SH events will be summarized.

Incidence rates of positively adjudicated SH events by treatment group and use of CSII at Screening (Yes, No) will be presented for the Double-blind Treatment Period.

Change from Baseline in hypoglycemic events calculated as a daily average over the week prior to the visit will be analyzed as a continuous variable as described in [Section 6.8.4.12](#). Since these data also serve as a measure of safety, additional analyses will be conducted. The first analysis of hypoglycemic events will be conducted using CMH tests stratified by the randomization factors at each clinic visit. These tests will provide inferential and descriptive summaries of the relative risk estimate for each of the 2 hypoglycemic event definitions: ≤ 70 mg/dL and ≤ 55 mg/dL by SMBG. The patient incidence of these hypoglycemic events will be counted over the week prior to the scheduled clinic visit used in the analysis. The second analysis of these data will examine the relative risk for each of the hypoglycemic event definitions over the entire Double-blind Treatment Period by use of a generalized linear model (GLM). The GLM will include fixed, categorical effects of treatment; BMI at Screening (< 25 kg/m², ≥ 25 kg/m²), Week -2 A1C ($\leq 9\%$, $> 9\%$), use of CSII at Screening (Yes, No), and an offset term for ~~treatment duration~~

Statistical Analysis Plan

Version: Final 1.0

Lexicon Pharmaceuticals Protocol No. LX 4211.1-312-T1DM

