7 CHANGES IN THE PLANNED ANALYSES OF THE PROTOCOL

- The protocol (Section 10.3.1.3) stated that the secondary endpoints (A1C, body weight, SBP, and bolus insulin dose) will be assessed at specified cut points. The specific cut points to use are provided in this SAP (see [Section 3.1.3](#)).

Statistical Analysis Plan

Version: Final 1.0

Lexicon Pharmaceuticals Protocol No. LX 4211.1-312-T1DM

Date of Issue: 17 MAR 2017

Covance Study ID: 000000145143

- Sensitivity analysis of the primary efficacy endpoint using the Last Observation Carried Forward (LOCF) algorithm to impute missing data will not be performed. The analysis of the primary efficacy endpoint will use NRI to impute missing data at Week 24 (see [Section 5.2.1](#)).
- Two sensitivity analyses of the primary efficacy endpoint using the same cut-off dates for SH and DKA events have been added (see [Section 6.8.2](#)).
- Summary statistics of mean bolus insulin dose, total daily insulin dose, and mean daily basal (or non-bolus) insulin dose as percent of the Baseline measure will be provided, as stated in [Sections 6.8.3.4](#) and [6.8.4.8](#).
- Analysis of the primary efficacy endpoint and the change from Baseline to Week 24 in A1C will be performed for the subgroups defined by age at study entry (<75 years, ≥75 years), sex, race, and Week -2 A1C (≤8.5%, >8.5%).
- Analysis of SBP change from Baseline to Week 16 will be performed for the subgroups defined by Baseline SBP <130 mm Hg, <140 mm Hg, and ≥ 140 mm Hg.
- EOSI events will be summarized by treatment groups across all patients (planned) and for the subgroups determined by use of CSII at Screening (Yes, No).
- For EOSIs of Malignancies of special interest, “thyroid” has been added to the list of malignancies in [Section 6.9.2](#).
- Amputations have been added to the EOSIs specifically listed in [Section 6.9.2](#) (note: per Section 9.5 of the protocol, AEs other than the EOSIs listed in the protocol may be determined to be of special interest).
- Additional overall summaries will be presented for EOSI for 3 time periods described in [Section 6.9.2](#).
- Incidence of BHB >0.6 mmol/L during Double-blind Treatment Period will be analyzed by logistic regression models.
- Incidence of treatment-emergent acidosis-related AEs will be analyzed.

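### The severe hypoglycemia precision statement behind 700 per arm holds with about 86% probability at the 0.10 planning ceiling, and the SAP text plans no confidence interval for that difference

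*SAP*

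**What the plan says.** **Sample size.** SAP 2.3 derives the primary endpoint requirement first: "Based on this adjusted effect size, 544 patients are required per treatment group". It then turns to SH and says the sample should be large enough that "a reliable estimate of a treatment difference can be obtained for this outcome". The planning conditions are an SH proportion of at most 0.10 over 24 weeks in mITT patients, the same rate in both arms, and an expected difference of 0.0. For 700 per arm it gives a half-width of 0.033 for a continuity-corrected two-sided 95% interval, measured from the observed difference. It concludes: "The upper bound of this CI will exclude values greater than 0.05", and describes 0.05 as half of the expected placebo rate. Protocol 10.1 and the protocol synopsis carry the same sentence.

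**Planned analysis of SH.**
- SAP 6.8: "Endpoints comprised of multiple outcomes will use descriptive methods to summarize each component by treatment group at each study week".
- SAP 6.8.1, on the primary composite: "The individual components of the endpoint will be summarized separately using descriptive methods". SAP 6.1 defines descriptive statistics for categorical variables as counts and percentages.
- SAP 6.9.4 gives SH incidence, event rates and Kaplan-Meier plots. Its CMH analysis provides "inferential and descriptive summaries of the relative risk estimate for each of the 2 hypoglycemic event definitions", and those two definitions are SMBG at or below 70 and at or below 55 mg/dL. The negative binomial model uses the same two.
- Protocol 10.4.3 says hypoglycemic events, as defined in protocol 9.5.1 (which includes SH), will be analyzed by "methods described for binary, continuous, and other variables in" protocol 10.4.1.
- The only entry in SAP Section 7 that names SH is: "Two sensitivity analyses of the primary efficacy endpoint using the same cut-off dates for SH and DKA events have been added".

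**The concern.** A half-width measured from the observed difference makes the upper limit a random quantity. The plan gives the half-width and then states where the upper limit will fall, with no probability and no mention that the result depends on the observed difference. A reader would expect the trial to rule out an SH excess above 0.05 whenever the true rates are equal.

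This matters because SH precision is the stated reason for enrolling 156 more patients per arm than the primary endpoint needs (700 − 544). If the interval that justifies those patients is not among the planned outputs, it may not be reported, or its method may be chosen after unblinding.

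**Working it through.** **Inputs.** From SAP 2.3: n = 700 per arm; common SH rate p at most 0.10; true difference 0; two-sided 95% interval, normal approximation, continuity-corrected; limit of interest 0.05; 544 per arm for the primary endpoint.

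**Step 1: reproduce the plan's figure (p = 0.10).**
- SE = √(2 × 0.10 × 0.90 / 700) = 0.01604
- Half-width = 1.96 × 0.01604 + 1/700 = 0.03143 + 0.00143 = 0.0329

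This agrees with the stated 0.033.

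**Step 2: what the sentence requires.** The upper limit is below 0.05 only if the observed difference is below 0.05 − 0.0329 = 0.0171, or about 12 patients in 700. With 70/700 SH patients on placebo, using each outcome's own variance:

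| SH on sotagliflozin | Observed difference | Upper 95% limit |
|---|---|---|
| 70/700 | 0.0000 | 0.0329 |
| 81/700 | 0.0157 | 0.0496 |
| 82/700 | 0.0171 | 0.0512 |

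**Step 3: probability under the plan's own assumptions.** The normal approximation at p = 0.10 is Φ(0.0171 / 0.01604) = 0.857. For the exact value, sum the joint binomial probability over all pairs of counts for which (p1 − p0) + 1.96 × √(p1q1/n + p0q0/n) + 1/n is below 0.05:

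| Common true rate | P(upper limit < 0.05), 700 per arm |
|---|---|
| 0.10 | 0.858 |
| 0.09 | 0.888 |
| 0.08 | 0.917 |
| 0.05 | 0.986 |

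At 0.10 the chance of missing is 1 − 0.858 = 0.142, about 1 trial in 7. The probability rises as the rate falls, but 0.05 is a 50% increase only when the placebo rate is 0.10.

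**Step 4: compare with 544 per arm (p = 0.10).**
- SE = √(0.18 / 544) = 0.01819
- Half-width = 1.96 × 0.01819 + 1/544 = 0.0375
- Probability = Φ((0.05 − 0.0375) / 0.01819) = 0.754; exact enumeration gives 0.755

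If the observed difference is exactly zero, the upper limit is already below 0.05 at 544, and this is so from about 316 per arm. What separates 544 from 700 is the probability: about 75% against 86%.

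**Step 5: look for the interval in the analysis sections.** The 95% limits in SAP 6.8 are for binary efficacy endpoints. SH enters efficacy as a component of the composite, and components are descriptive. In the safety section the comparative models are confined to the two SMBG thresholds. Nowhere does the SAP text plan a confidence interval for the between-arm SH difference.

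**The case against.** **The sentence is conditional.** SAP 2.3 states its assumptions (rates at most 0.10, equal arms, expected difference 0.0) and says the half-width is measured from the observed difference. Read as an expected-precision statement, with the observed difference at its expected value, the upper limit is 0.033 and the sentence is true. This stands to the extent that the statement is not made without conditions and no computed figure in it is wrong. But on that reading the sentence does not support 700 over 544, because 544 satisfies it too.

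**86% is the worst case.** It is the lowest value over the assumed range and must be labelled so. It is also the rate at which the 50% description applies.

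**An SH interval may already be planned.** A reader might infer that the trial plans no between-group analysis of SH at all. The documents do not support that. Protocol 10.4.3 routes hypoglycemic events, SH included, to the methods of 10.4.1, and SAP Section 7 does not withdraw it, so it may still apply. Protocol 10.4.4 plans formal analysis of SH under separate meta-analysis plans, though only pooled with other trials. Table shells are in a file that the SAP says is not part of it. The absence can therefore be asserted only for the SAP text. In addition, the interval follows directly from the mITT counts that 6.8.1 will present, so the practical loss is small.

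**The definitions are not fully settled.** A reader might infer that only a table row is missing. In fact SAP 2.3 plans a 24-week rate and does not mention adjudication, whereas 6.8.1 counts positively adjudicated events up to the last dose. With 20% assumed to stop treatment early but be followed, these can differ, so the added analysis must say which it uses.

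**Conclusion.** The point holds as a minor one. At 700 per arm, with equal true SH rates and the continuity-corrected interval of SAP 2.3, the upper limit is below 0.05 with probability about 86% at a rate of 0.10, 92% at 0.08 and 99% at 0.05. These figures take all 700 patients per arm as contributing and a true difference of zero.

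Separately, the SAP text does not plan the interval that supports going beyond 544 per arm. It neither carries protocol 10.4.3 through for SH nor records dropping it.

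A reader might infer that the sample size is wrong or that the trial is underpowered. It is not so: the 0.033 is correct, and no test, margin, alpha, primary power or step of the testing hierarchy depends on the sentence.

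**What to change.** 1. **SAP 2.3.** Replace the sentence with: *700 per arm gives an expected half-width of 0.033 and about 86% probability that the upper 95% limit is below 0.05 if both true rates are 0.10 (about 92% at 0.08, 99% at 0.05); 0.05 is a 50% increase only if the placebo rate is 0.10.* Note the difference from the protocol text in SAP Section 7, and align protocol 10.1 and the synopsis at the next amendment.

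2. **SAP 6.8.1.** Add, as carrying out protocol 10.4.3 for SH, the LX4211-minus-placebo difference in the proportion of mITT patients with at least one positively adjudicated SH event, with its continuity-corrected 95% interval. Present it as an estimate, outside the testing hierarchy and without a formal margin. Use the last-dose cut-off of 6.8.1, state that the planning rate in 2.3 was for 24 weeks, and repeat with the 30-day cut-off of 6.8.2.

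**Cost.** The precision statement reads slightly less favourably, and the tables gain one or two rows. The SAP and protocol wording differ until the next amendment, which needs ethics committee approval in the usual way. No extra patients or data are needed, and sample size, alpha and hierarchy do not change.
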